### **5.5.9 Discontinuation of study treatment**

Study drug must be discontinued for a given patient if the investigator determines that continuing it would result in a significant safety risk for that patient. The following circumstances require study drug discontinuation:

- Emergence of the following adverse events:
  - in the case of any severe or serious adverse event that is not compatible with administration of study medication, including adverse events that require treatment with an unacceptable co-medication,
  - in the case of onset of malignancy,
  - in the case of an uncontrolled life-threatening infection.
- Pregnancy
- Use of the prohibited concomitant medications
- Withdrawal of informed consent

#### **5.5.10 Withdrawal of consent**

Subjects also should be withdrawn at any time if the investigator concludes that it would be in the patient's best interest for any reason. Protocol deviations should not lead to patient withdrawal unless they indicate a significant risk to the patient's safety.

Subjects may voluntarily withdraw from the study for any reason at any time. They may be considered withdrawn if they state an intention to withdraw, or fail to return for visits, or become lost to follow up for any other reason.

If premature withdrawal occurs for any reason, the investigator must determine the primary reason for a patient's premature withdrawal from the study and record this information on the Study Completion CRF. For subjects who are lost to follow-up (i.e., those subjects whose status is unclear because they fail to appear for study visits without stating an intention to withdraw), the investigator should

show "due diligence" by documenting in the source documents steps taken to contact the patient, e.g., dates of telephone calls, registered letters, etc.

Every patient has the right to discontinue study participation at any time, and every patient may be discontinued from the study for any reason beneficial to his/her wellbeing. All data generated up to the time of discontinuation from the study will be analysed and the reason(s) for discontinuation will be recorded.

#### **5.5.11 Loss to follow-up**

For patients whose status is unclear because they fail to appear for study visits without stating an intention to withdraw, the investigator should show "due diligence" by contacting the patient, family or family physician as agreed in the informed consent and by documenting in the source documents steps taken to contact the patient, e.g. dates of telephone calls, registered letters, etc. A patient should not be formally considered lost to follow-up until his/her scheduled end of study visit would have occurred.

#### **5.5.12 Emergency breaking of assigned treatment code**

Not applicable

#### **5.5.13 Study completion and post-study treatment**

Information on the date the subject last took drug, the subject's completion or discontinuation of the study and the reason for discontinuation of the study will be recorded on the Study Completion CRF page.

Visit	Screening ***	1***	2	3	4	5	6	7	8	9	10	11	12	13	14	15
Day	-7 to 0	0	7	14	30	60	90	120	150	180	210	240	270	300	330	360
Blood biochemistry		X		X	X			X	X	X	X	X				
Inflammatory markers	X	X	X	X	X	X	X	X	X	X	X	X	X	X	X	X
Urine Test	X	X	X	X	X	X	X	X	X	X	X	X	X	X	X	X
PK markers		X	X		X	X	X			X		X				X
PD samples		X	X		X	X	X			X		X				X
MR-Doppler Imaging (PET-CT when necessary)		X	X	X	X	X	X			X		X				X
(*)CSF Puncture	X			X	X		X									
Neurological evaluation		X	X	X	X	X	X	X	X	X	X	X	X	X	X	X
BDCA (BD Current Activity)	X	X	X	X	X	X	X	X	X	X	X	X	X	X	X	X
Adverse Events	X	X	X	X	X	X	X	X	X	X	X	X	X	X	X	X
VAS for symptoms	X	X	X	X	X	X	X	X	X	X	X	X	X	X	X	X
Efficacy Assessment					X		X			X						X
Attack Assessment	X	X	X	X	X	X	X	X	X	X	X	X	X	X	X	X
Steroid usage assessment	X	X	X	X	X	X	X	X	X	X	X	X	X	X	X	X
Physician&Patient Global Assessment		X	X	X	X	X	X	X	X	X	X	X	X	X	X	X
Drug Administration		X			X	X	X	X	X	X	X	X	X	X	X	X

\*Optional

\*\* PPD test could be used within 6 months before patient study entry

**\*\*\* If needed, in Patient's emergency situation, Screening and Visit 1 assessment could be combining by the physician decisions. There is no need to be repeated same test for each visit (screening and visit 1)**

## 5.6 Information to be collected on screening failures

All patients who have signed informed consent but not entered into the next epoch will have the study completion page for the screening epoch, demographics, inclusion/exclusion, and SAE data collected. Adverse events that are not SAEs will be followed by the investigator and collected only in the source data.

For all patients who have signed informed consent and are entered into the next epoch of the study will have all adverse events **occurring after informed consent is signed** recorded on the Adverse Event CRF.

Investigators will have the discretion to record abnormal test findings on the medical history CRF whenever in their judgment, the test abnormality occurred prior to the informed consent signature.

## 5.7 Patient demographics/other baseline characteristics

Patient demographic and baseline characteristic data to be collected on all patients include: date of birth, age, sex, ethnicity, patient referral source, relevant medical history/current medical condition present before signing informed consent. Where possible, diagnoses will be recorded, not symptoms.

Subjects should be seen for all post-baseline visits on the designated day with the allowance of a  $\pm 7$  day window for all visits. Subjects who discontinue study drug before completing the study, and those who prematurely withdraw from the study for any reason, should be scheduled for a visit 8 weeks ( $\pm 1$  week) after their last infusion /injection, at which time all of the assessments listed for the final visit will be performed.

Subjects who discontinue study drug also should return for a last assessment. If they refuse to return for this or are unable to do so, every effort should be made to contact them or a knowledgeable informant by telephone to determine the reason for discontinuation. At a minimum, they will be contacted for safety evaluations during the 30 days following the last dose of study drug, including final contact at the 30-day point. Documentation of attempts to contact the patient should be recorded in the patient record.

Information that will be collected on subjects who are screened but not enrolled includes patient demographics (age, gender, and ethnicity) and primary reason for not continuing.

If a patient discontinues before entering Visit 1, only the demographic information and Screening Log entry with the primary reason for discontinuation should be completed on the CRF. It is not necessary to complete all the required evaluations at the time of discontinuation unless medically indicated.

At screening visit information on age, sex, will be collected. Relevant medical history/current medical conditions, family medical history, will be recorded on the respective CRF page. The following should be recorded on the respective CRF page.

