### **5.5.6 Rescue medication**

A rescue treatment with increased doses of prednisolone or intravenous methyl prednisolone pulses could be used depending on worsening of BD manifestations at the discretion of the investigator.

If no response or worsening of neurologic/vascular manifestations were observed in the first week, rescue treatment decision should be given with the repeated CSF and MRI (neurologic) or CT/Doppler (vascular) analyses.

Following protocol will be used as rescue treatment in patients with worsening symptoms:

For patients with neurologic involvement: 5-10 days of 1000 mg intravenous methyl prednisolone, followed by 1 mg/kg/day prednisolone, if still an insufficient response is observed, 1000 mg intravenous cyclophosphamide

For patients with vascular involvement: 3 days of 1000 mg intravenous methyl prednisolone, followed by 1 mg/kg/day prednisolone, if still an insufficient response is observed, 1000 mg iv cyclophosphamide.

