### 5.10.7 Pharmacokinetics

All blood samples will be taken by either direct venipuncture or an indwelling cannula inserted in a forearm vein. It is important to note that the volume of blood sampling will be adapted to the age of the child according to clinical practice at the investigator site. For each scheduled PK sample, 2 mL of blood will be drawn into a plain barrier tube to obtain 1 ml serum. The sample will be allowed to clot during 45 minutes at room temperature. The serum will be obtained by centrifugation at approximately 2500 g for 10 minutes. The sample will be split into two aliquots to be transferred into polypropylene screw-cap tubes. Serum tubes will be frozen within 90 min of venipuncture and kept at  $\leq -18^{\circ}\text{C}$  pending analysis. One of the two serum samples is to be kept at the study site as a backup while the other one will be shipped to the analytical center.

Time points for canakinumab PK sample collection at Visits:

- Day 0 (Visit 1)
- Day 7 (Visit 2)
- Day 30 (Visit 4); pre-dose
- Day 60 (Visit 5); pre-dose
- Day 90 (Visit 6) pre-dose
- Day 180(Visit 9) pre-dose
- Day 240(Visit 11) pre-dose
- Day 360 (Visit 15) pre-dose

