#### **5.10.7.2 PK sample handling, labeling and shipment instructions**

##### **5.10.7.2.1 Sample labeling**

Serum tubes will be used to collect samples.

The samples for the pharmacokinetic profile will be labeled as follows:

PK

Study Code: CACZ885NTR01

Subject Number:

Sample Number:

Date / Study Day:

Labels will be provided to the investigator with all label information preprinted on the label.

The actual sample collection date and exact time will be entered on the PK Blood Collection

Log CRF page. Sampling problems will be noted on the PK Blood Collection Log CRF

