### **8.5.3 Pharmacokinetics**

A mixed effects modeling approach will be taken in order to analyze the complete PK data from the study. Quality of individual fits to the dataset will be assessed and if the fits are apparently unbiased, the model derived population pharmacokinetic model parameter mean and inter-individual variance-covariance matrices of parameters such as CL (clearance), V

(apparent volume of distribution),  $k_a$  (first-order absorption rate constant) and withinindividual variance will be estimated. In addition, posthoc estimates of the same parameters, i.e. CL, and V will be reported for each individual.

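### The ±7-day window for all post-baseline visits makes Visits 2 (Day 7) and 3 (Day 14) overlap, so the only two looks between baseline and Day 30 can coincide or swap order (low severity)

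*Combined protocol and SAP*

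**What the plan says.** Section 5.7 sets a single visit tolerance: "Subjects should be seen for all post-baseline visits on the designated day with the allowance of a" ±7 "day window for all visits". It makes no exception for the early visits or for PK/PD visits.

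The assessment schedule (printed under Section 5.5.13) places Visit 1 on Day 0, Visit 2 on Day 7, Visit 3 on Day 14 and Visit 4 on Day 30, with visits every 30 days after that. The row "Drug Administration" is marked at Visit 1 and Visits 4-15, and not at Visits 2 and 3. Imaging, inflammatory markers, neurological evaluation, symptom VAS and global assessments are marked at both Visit 2 and Visit 3.

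PK and PD samples are scheduled on Days 0, 7, 30, 60, 90, 180, 240 and 360. The PK list in Section 5.10.7 marks the samples from Day 30 onward as pre-dose, for example "Day 30 (Visit 4); pre-dose".

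Section 2.2 lists two secondary endpoints that depend on when resolution is first seen: time to at least 50% resolution of the MRI lesion (neurologic) and time to resolution (vascular).

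**The concern.** A visit window should be narrower than the spacing of the visits it governs. Here it reaches 7 days either side of visits that are 7 days apart. A site can follow the protocol exactly and still hold Visits 2 and 3 together, or hold Visit 3 first.

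Two things are at stake. First, resolution on imaging can only be dated to the visit at which it is first seen. Visits 2 and 3 are the only scheduled imaging and clinical looks between baseline and Day 30. If they merge, two planned observations become one, and the early part of the time-to-resolution data becomes coarser. Second, Visit 2 provides the one scheduled on-treatment PK/PD sample away from a dosing visit, at most one per patient in a study of about 10 patients. The plan has little control over where in the first two weeks that sample falls.

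**Working it through.** The plan gives no derivation of its window, so there is no figure to reproduce. The check is interval arithmetic on the schedule's own days.

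**Inputs.** Window w = 7 days (Section 5.7). Nominal days: Visit 1 = 0, Visit 2 = 7, Visit 3 = 14, Visit 4 = 30, then every 30 days to Visit 15 = 360 (assessment schedule).

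**Step 1: permitted days (nominal day − w to nominal day + w).**

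- Visit 2: 7 − 7 = 0 to 7 + 7 = 14.
- Visit 3: 14 − 7 = 7 to 14 + 7 = 21.
- Visit 4: 30 − 7 = 23 to 30 + 7 = 37.

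**Step 2: overlap.** Visits 2 and 3 share Days 7 to 14, which is 14 − 7 + 1 = 8 calendar days. Visit 3 ends on Day 21 and Visit 4 opens on Day 23, so they do not meet. Later visits are 30 days apart and 2 × 7 = 14 < 30, so none of them overlap. Visits 2 and 3 are the only overlapping post-baseline pair.

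**Step 3: what the rule permits.** Each window has 15 days, giving 15 × 15 = 225 day pairs. Visit 3 falls on or before Visit 2 in 1 + 2 + … + 8 = 36 of them: 8 on the same day and 28 in reverse order. This counts permitted combinations. It is not a probability, because Day 7 and Day 14 remain the targets.

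**Step 4: effect on the early imaging looks.** Assume baseline imaging on Day 0 and Visit 4 on Day 30. At nominal timing the gaps between looks are 7, 7 and 16 days. If Visits 2 and 3 fall on one day d, with d from 7 to 14, there are two gaps, d and 30 − d. These are 7 and 23 days at d = 7, and 14 and 16 days at d = 14.

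**Step 5: PK/PD.** Setting the sampling visits (1, 2, 4, 5, 6, 9, 11, 15) against the dosing visits (1 and 4-15) leaves Visit 2 as the only sampling visit without dosing. By the window, its sample may be taken anywhere up to Day 14.

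**Step 6: the widest symmetric window without overlap.** Visits 7 days apart need 7 + w < 14 − w, so 2w < 7 and w ≤ 3 in whole days.

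- w = 3: Days 4-10 and Days 11-17, no shared day.
- w = 4: Days 3-11 and Days 10-18, which share Days 10 and 11.

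Any w of 6 or less also keeps Visit 2 off Day 0.

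**The case against.** The overlap itself cannot be disputed, but several larger harms that a reader might infer from it are not supported.

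- **Spoiled Day 7 and Day 14 summaries.** None is planned. Section 8.6 sets the analyses at Days 30, 90, 180 and 360, Section 5.9.3 uses the same days for BDCAF, and the primary endpoint is read at Day 30. This objection stands in full.
- **Visit 2 held on the day of the first infusion.** Day 0 is arithmetically the edge of the window, but the window covers post-baseline visits and Section 5.5.8 calls Day 0 the baseline visit. This is a doubtful edge case and nothing should rest on it.
- **Loss of the PK/PD information.** The sample is still taken, with Day 7 as its target. Section 5.10.7.2.1 requires that "The actual sample collection date and exact time will be entered on the PK Blood Collection" log, and Section 5.10.8.2.1 asks the same for PD. Section 8.5.3 states: "A mixed effects modeling approach will be taken in order to analyze the complete PK data from the study". Such a model uses actual times, and the documents name no Day 7 PK parameter that another day would make wrong. What is left is weak control over where one sample falls. The sample is also unique only among scheduled on-treatment samples, because patients who stop early have the final-visit assessments, PK and PD included, 8 weeks after their last dose.
- **A missed first-week rescue assessment.** Section 5.5.6 reads "If no response or worsening of neurologic/vascular manifestations were observed in the first week, rescue treatment decision should be given" with repeat CSF and imaging. It does not name Visit 2, and the schedule marks no CSF puncture at Visit 2, so the link is only an inference. The decision could be made at an unscheduled contact. It is still true that Visit 2 is the only scheduled visit whose nominal day falls in that week, and that a compliant Visit 2 on Days 8-14 comes after it. That supports a request to reconcile the two sections and nothing more.

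It can also be said that ±3 days is not the only cure. Asymmetric windows, or a rule that keeps the visits in order on separate days, would also work. That is correct, and ±3 is offered only as an example.

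**Conclusion.** The point holds at low severity. One stated rule, applied to the schedule's own days, lets two planned early visits coincide or swap order over an 8-day stretch, and nothing elsewhere in the document corrects it. The consequence is confined to the early resolution of the time-to-resolution secondary endpoints and to loose placement of one PK/PD sample per patient. The primary endpoint and the planned analysis days are not affected.

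This rests on reading the window literally as ±7 days for Visits 2 and 3, and on time to resolution being taken from scheduled visits. The document gives no method for that endpoint: Section 8.5.1 names Kaplan-Meier estimates only for time to relapse. How often sites would use the extremes of the window cannot be known from the documents.

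**What to change.** Add one sentence to Section 5.7 giving Visits 2 and 3 their own windows, which do not overlap and which fall after Day 0. An example is ±3 days, that is Days 4-10 for Visit 2 and Days 11-17 for Visit 3. This secures two separate looks in the right order. It does not guarantee a 7-day gap, since Days 10 and 11 would both be allowed; a minimum spacing could be added if that matters.

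The cost is slightly tighter scheduling of two visits. Neither is a dosing visit, so no dose or dosing interval changes. No view is taken here on the window for the dosing visits.

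Separately, the sponsor should reconcile the visit window in Section 5.7 with the first-week wording in Section 5.5.6 and say whether Visit 2 is meant to serve that assessment. Even a ±3-day window allows Visit 2 as late as Day 10, so narrowing the window does not settle this. No clinical rule is proposed.

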### 5.7.1 Laboratory tests

The investigator will evaluate the clinical significance of each laboratory value outside of the reference range. This decision should be based upon the nature and degree of the observed abnormality. The investigator may choose to repeat any abnormal result ONCE, in order to rule out laboratory error. "NCS" will be entered on the original laboratory sheet to the right of

all laboratory values, which are outside the reference range, but are judged "not clinically significant." The physician making these assessments should date and initial each form. A copy of each laboratory report must be placed in the patient's file. Clinically relevant deviations of laboratory test results occurring during or at completion of the study must be reported and discussed with Novartis. Repeated evaluations are mandatory until normalization or until the change is no longer clinically relevant. In case of doubt, Novartis must be contacted.

All laboratory tests will be performed in the study site except PK/PD, [REDACTED]  
[REDACTED]  
[REDACTED]  
[REDACTED]  
[REDACTED]  
[REDACTED]  
[REDACTED]  
[REDACTED]

### **5.7.2 Inflammation markers**

The following markers of inflammation, Erythrocyte Sedimentation Rate (ESR), C-reactive protein (CRP) and serum amyloid A (SAA), will be performed at all scheduled visits.

### **5.7.3 Hepatitis screen, HIV screen**

In order to exclude an active hepatitis B or C or HIV infection, all subjects will undergo appropriate testing at the screening visit and. All subjects will be screened for Hepatitis B surface antigen (HBsAg). Screening for Hepatitis C will be based on HCV antibodies. A copy of the lab report must be placed in the patient's file. Evaluation for HIV seropositivity will consist of ELISA and, if positive, confirmation by Western blot will be required. Appropriate subject counselling will be made available by the investigator in the event of a positive finding. Notification of state and federal authorities, as required by law, will be the responsibility of the investigator. A copy of the lab report must be placed in the patient's file.

### **5.7.4 Latent tuberculosis infection screening**

Latent tuberculosis infection screening will be performed by a PPD skin test by intradermal injection of 5 tuberculin units of standard PPD, and/or interferon-gamma release assay such as Quantiferon-Gold assay at screening visit or within 6 months before patient study entry, and the results will be evaluated at screening visit before the first dose of study medication. A PPD skin induration at 72 hours of  $\geq 5$  mm is interpreted as a positive result. If PPD test or Quantiferon-Gold assay result shows latent TB infection without signs of active tuberculosis disease, patient will be allowed to enter the study in the study, if the patient is taking isoniazid prophylaxis before the study drug administration and agrees to continue the prophylaxis for 9 months.

Also because of natural life threatening course of neurological and vascular involvements, in patients who need an urgent intervention, drug administration can be started without waiting test results of PPD or Quantiferon assay if there are no findings of active tuberculosis disease. If but test results confirm a latent TB infection without signs of active tuberculosis, patients should start taking INH prophylaxis treatment for 9 months along with the study drug administration.

### **5.7.5 Chest X-ray**

In the event of a positive PPD skin test result at screening, or prior BCG immunization, or history of treated tuberculosis, a chest X-ray will be obtained, if one has not been administered during the 12 months before the first dose of study medication to assess the tuberculosis status of the patient. If a chest X-ray has been obtained in the previous 12 months, a chest X-ray may be ordered at the investigator's discretion, based on the patient's clinical picture and local standard of medical care. Any significant findings will be recorded in the "Relevant medical history/Current medical conditions" section of the CRF as necessary.

## **5.8 Treatment exposure and compliance**

Any deviations from the protocol regarding the administration of study medication must be described on the Dose Administration Record CRF.

Concomitant medications/ non-drug therapy before the first dose of study medication and after start of study drug will be collected, including medication name and reason.

## **5.9 Efficacy**

### **5.9.1 Resolution of Attacks**

#### **The definition of the attack**

**For Vascular Disease:** Recent Onset symptomatic Venous Thrombosis or Arterial Aneurysm.

**For Neurologic Disease:** An acute/subacute neurological syndrome including any of hemiparesis, ataxia, dysarthria within the first month of onset of neurologic manifestations.

**Primary endpoint:** Resolution of acute exacerbation findings related to BD based on achievements in any of the following items without deterioration on day 30:

#### **1-For Neuro Behcet Attack**

- A Improvement of muscle strength (Measured by MRC, and VAS)
- B Ataxia (Measured by global assessment of Physician)
- C Modified EDSS (Modified Expanded Disability Status Scale) , Neuro-Behçet's Disability Score (NBDS) **ranging from 0-8 and the modified Rankin scores (0-6)**
- D Improvement in systemic inflammatory findings (CRP, ESR, SAA)
- E Any decrease in the size of the MRI lesion, or disappearance of contrast enhancement

**Complete response** will be defined as full clinical recovery to pre-attack state, disappearance of MRI lesion(s), CSF becomes normal.

**Partial response** will be defined as partial improvement in clinical findings, but with findings still worse than pre-attack state, MRI lesions which become smaller with no or less enhancement, and a decrease in CSF cell count.

**Non-response** will be defined as no improvement in clinical findings, no change on MRI, no change in CSF parameters, or worsening in those findings.

